6.10.4 Relationship

The Investigator will assess the relationship of the AE to DEFINITY®. The following categories and definitions of causal relationship should be used for this study:

- **Not related:** indicates that there is little or no chance that the study treatment or procedure caused the reported AE; other conditions, including concomitant illnesses, progression or expression of the disease state, or a reaction to a concomitant medication, appear to explain the reported AE. For the purposes of determining expedited reportability, AEs categorized as unlikely related to investigational product will not be considered associated with the investigational product.
- **Possibly related:** indicates that the association of the AE with the study treatment or procedure is unknown; however, the AE is not reasonably attributed to any other condition
- **Related:** indicates that a reasonable temporal association exists between the AE and study treatment or procedure and, based upon the investigator's clinical experience, the association of the event with the study treatment seems likely

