6.10.6.2 Reporting Serious Adverse Events

All SAEs, whether related or unrelated to the investigational product, must be reported within 1 calendar day to LMI Drug Safety by confirmed facsimile transmission, email or phone. Overnight express mail may also be used in lieu of a facsimile transmission. If only limited information is initially available, follow-up reports are required. The original SAE form must be kept on file at the study site.

Collection of complete information concerning SAEs is extremely important. Thus, follow-up information that becomes available as the SAE evolves, as well as supporting documentation (e.g., hospital discharge summaries and autopsy reports), should be collected subsequently, if not available at the time of the initial report, and immediately sent using the same procedure as the initial SAE report.

The contact information for reporting SAEs and follow-up SAE information is:

Contact	Telephone Number	Fax Number	Email Address
LMI Safety	[name] + [contact]	[contact]	[contact]

If the investigator needs to discuss an SAE or any other aspect of the protocol with the Medical Monitor, s/he can be reached at the following numbers:

LMI Medical Monitor
24-Hour [contact]
[contact]

In the event of AEs that are serious, unexpected, and possibly related or related to DEFINITY® administration, LMI will contact the Investigator and will provide a MedWatch and/or Council for International Organizations of Medical Sciences (CIOMS) narrative of the case, which will include an Analysis of Similar Events. The Investigator is responsible for notifying the appropriate IRB in accordance with institutional requirements. The Investigator and IRB will determine if the IC requires revision. The Investigator should also comply with the IRB procedures for reporting any other safety information.

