9.3. Adverse Events

A treatment-emergent adverse event (TEAE) is an AE that started or worsened in severity following the start of administration of DEFINITY®. A table of AEs will be summarized for the following:

- Number of subjects having experienced at least one TEAE
- Number of subjects having experienced at least one TEAE related to DEFINITY®
- Number of subjects having experienced at least one TEAE related to study procedure
- Number of subjects having experienced at least one severe TEAE
- Number of subjects with study procedure interrupted due to a TEAE
- Number of subjects with study procedure interrupted due to a TEAE related to DEFINITY®
- Number of subjects with study procedure interrupted due to a TEAE related to the study procedure
- Number of subjects having experienced at least one serious TEAE
- Number of subjects having experienced at least one serious TEAE related to DEFINITY®
- Number of subjects having experienced at least one serious TEAE related to a study procedure
- Number of subjects having experienced at least one severe serious TEAE
- Number of subjects with study procedure interrupted due to a serious TEAE
- Number of subjects with study procedure interrupted due to a serious TEAE related to DEFINITY®
- Number of subjects with study procedure interrupted due to a serious TEAE related to the study procedure
- Number of subjects having experienced a fatal TEAE
- Number of subjects having experienced a fatal TEAE related to DEFINITY®
- Number of subjects having experienced a fatal TEAE related to the study procedure

If an AE is described as being 'related to DEFINITY®', unless otherwise stated, this will be defined as a relationship to DEFINITY® administration where the relationship is defined as either possibly related or related. If an AE is described as being 'related to study procedure', unless otherwise stated, this will be defined as a relationship to DEFINITY® enhanced echo and/or DEFINITY® administration and/or unenhanced echo and/or CMR where the relationship is defined as either possibly related or related.

This document is confidential.

A summary table of TEAEs (number and percentage of subjects who experienced an AE and number of events) grouped by primary SOC and PT will be presented for the following categories of events:

- All TEAEs
- All TEAEs related to DEFINITY®
- All TEAEs related to study procedure
- All serious TEAEs
- All serious TEAEs related to DEFINITY®
- All serious TEAEs related to study procedure

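### The protocol's causality scale has no clearly fitting category for an adverse event that DEFINITY plausibly but not likely caused and that another condition could also explain

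*Protocol*

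**What the plan says.** Protocol 6.10.4 opens with the instruction "The Investigator will assess the relationship of the AE to DEFINITY" and then defines three levels.

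- *Not related* "indicates that there is little or no chance that the study treatment or procedure caused the reported AE"; it continues that "other conditions, including concomitant illnesses, progression or expression of the disease state, or a reaction to a concomitant medication, appear to explain the reported AE".
- *Possibly related* applies when the association with treatment or procedure "is unknown; however, the AE is not reasonably attributed to any other condition".
- *Related* needs a reasonable association in time and that, "based upon the investigator's clinical experience, the association of the event with the study treatment seems likely".

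The *Not related* entry also carries a rule on expedited reporting: "AEs categorized as unlikely related to investigational product will not be considered associated with the investigational product".

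Three places use the rating.

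- **SAP 9.3** counts an AE as related to DEFINITY, or to a study procedure, "where the relationship is defined as either possibly related or related".
- **Protocol 8.4.1** tabulates AEs that are at least possibly related to study procedures.
- **Protocol 6.10.6.2** ties the sponsor's MedWatch/CIOMS narrative to the same two levels: "In the event of AEs that are serious, unexpected, and possibly related or related to DEFINITY® administration".

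**The concern.** A three-level scale should place the uncertain event in the middle. Here the middle level is the only one that makes the absence of another explanation a condition of entry. The top level does not ask for it. On the question of competing causes, *Possibly related* is therefore stricter than *Related*.

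The gap concerns an event that will plausibly occur in this trial. Protocol 3.2 describes a population with known or suspected cardiac disease, and three of the four target LVEF groups lie at or below 50%. Dyspnoea soon after injection in a subject with LVEF below 30% is an example: the drug could be responsible, and so could the heart disease.

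The investigator's rating also carries much of the drug attribution. There is one treatment group, so no untreated arm gives a background rate. Vital signs are taken at screening only, and no data monitoring committee is formed. If investigators place the same kind of event in different categories, the related-AE counts depend partly on who did the rating.

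**Working it through.** The documents give no AE rate or other figure on this point, so the check is one of logic. Take an AE with two reasonable explanations, DEFINITY and an underlying condition, and test it against each definition in protocol 6.10.4.

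**Case A: DEFINITY plausible but not judged likely**

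| Category | Condition | Met? |
|---|---|---|
| *Not related* | Little or no chance of causation | No, because the drug is plausible |
| *Not related* | Other conditions appear to explain the event | Arguably yes |
| *Possibly related* | Association unknown | Yes |
| *Possibly related* | Event not reasonably attributed to another condition | No, on the natural reading |
| *Related* | Reasonable timing | May be yes |
| *Related* | Link seems likely | No, by construction |

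Each category fails on at least one condition, so none clearly fits.

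**Case B: DEFINITY judged likely, timing reasonable.** *Related* applies, because it does not ask for other causes to be ruled out. The gap is therefore confined to Case A.

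**Where a Case A event goes under each coding**

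| Output | Coded *Not related* | Coded *Possibly related* | Left blank |
|---|---|---|---|
| DEFINITY-related rows, SAP 9.3 | Out | In | In (SAP 9.3 counts missing as related) |
| MedWatch/CIOMS wording, protocol 6.10.6.2 | Not met | Met if serious and unexpected | Not addressed |
| All-TEAE tables, SAP 9.3 | In | In | In |
| Serious-TEAE tables, SAP 9.3 | In if serious | In if serious | In if serious |
| SAE report to sponsor within 1 calendar day | Yes if serious | Yes if serious | Yes if serious |

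The procedure-related rows of SAP 9.3 and the tabulation in protocol 8.4.1 use the same threshold. An event rated *Not related* to the procedures drops out of both.

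**The expedited-reporting sentence.** It governs events rated unlikely related. The scale has three levels, and that is not one of them. The sentence sits inside the *Not related* entry, which suggests where it was meant to apply.

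**Drug and procedure.** The lead-in asks about DEFINITY. The first two definitions refer to treatment or procedure together. *Related* mentions both for timing but only treatment in its final clause. Protocol 6.10.1 asks for an opinion on drug, procedure and underlying disease and points to these definitions, which do not separate the three. SAP 9.3 needs the attributions apart: DEFINITY administration on its own, and a procedure grouping that adds enhanced echo, unenhanced echo and CMR.

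**The case against.** The strongest reply rests on one word. The text says attributed, not attributable. If an investigator sees two plausible causes and cannot choose between them, the association is unknown and the event has not been attributed elsewhere, so *Possibly related* is open. That reading is available. It is not the only one, and nothing in the protocol tells sites to adopt it. The point that two careful investigators could code the same event differently therefore stands.

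The consequences are limited, and this part of the reply stands in full. Every serious AE goes to the sponsor whatever its causality, and the SAP tabulates all TEAEs and all serious TEAEs regardless of relationship. Protocol 6.10.6.2 does not say that the investigator's rating alone decides the MedWatch/CIOMS step.

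A reader might infer that the scale pushes these events into *Not related* and so biases the drug-related rates downward. The documents do not show this. *Not related* is the only definition that mentions concomitant illness and disease progression, which makes such coding plausible, but no rule sends the events there and its first condition excludes them.

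A reader might also see a conflict with the SAP, which counts a missing relationship as related. There is none: one rule covers missing ratings and the other covers recorded ones.

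Finally, a reader might conclude that drug and procedure attributions are not collected separately. Protocol 6.10.1 and SAP 9.3 both presuppose that they are, and the eCRF is not among the documents. What can be said is that the definitions in 6.10.4 do not match that structure.

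**Conclusion.** The definitions leave a real gap, limited to events for which DEFINITY is plausible but not likely and another condition is also a reasonable explanation. The foreseeable result is inconsistent coding across about 10 centers. Any event of this kind coded *Not related* leaves the related-AE tables and falls outside the MedWatch/CIOMS wording. It is not lost from overall safety reporting, and the primary efficacy analysis is unaffected.

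The size of any under-count cannot be computed. A reader might try assumed rates: if 10 of 150 subjects had a TEAE for which the drug was plausible, 10/150 = 6.7%. If 50% to 80% of those also had another plausible cause and were all coded *Not related*, 5 to 2 would remain, or 5/150 = 3.3% to 2/150 = 1.3%. The arithmetic is right, but every input is an assumption, including that all such events are coded *Not related*. Protocol 4.2 also excludes unstable cardiovascular status, so the LVEF groups alone do not show how often competing causes will arise.

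The conclusion rests on the natural reading of the *Possibly related* definition. On the looser reading a category exists, but the protocol does not say that this reading applies. The unlikely-related label is a separate, smaller defect that holds on either reading.

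**What to change.** In protocol 6.10.4:

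1. Reword *Possibly related* to cover events where a causal role cannot be excluded, even though another condition could also explain the event.
2. Keep *Not related* for events with little or no chance of causation, and say that another possible explanation is not enough by itself.
3. Map the unlikely-related sentence to *Not related*, or delete it.
4. State that relationship to DEFINITY and relationship to the study procedures are rated separately, and word each definition so that it can be applied to either, in line with SAP 9.3.

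The cost is a few sentences of protocol text and matching eCRF completion guidance. An added eCRF field is needed only if the form does not already hold the separate ratings. The downside is that somewhat more events will be reported as possibly related.

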6.10.5 Clinical Significance

Any abnormality in physical examinations or vital signs not present at Baseline should be judged for clinical significance by the Investigator.

6.10.6 Serious Adverse Events

6.10.6.1 Definition

A serious adverse event (SAE) is defined by regulation as any AE occurring at any dose that results in any of the following outcomes:

- Death
- Life-threatening AE
- In-patient hospitalization or prolongation of existing hospitalization
- Persistent or significant disability/incapacity, or
- Congenital anomaly/birth defect.

Important medical events that may not result in death, be life threatening, or require hospitalization may be considered an SAE when, based upon appropriate medical judgment, they may jeopardize the patient and may require medical or surgical intervention to prevent one of the outcomes listed in this definition. Examples of such medical events include

allergic bronchospasm requiring intensive treatment in an emergency room or at home, and blood dyscrasias or convulsions that do not result in inpatient hospitalization.

Note: Hospitalization for scheduled elective procedures or hospitalization from clinically indicated patient management decisions based on pre-study conditions should not be classified as SAEs. Examples of this would include a scheduled coronary intervention or CABG procedure within the SAE reporting period. Additionally, a treatment procedure scheduled due to diagnosis during the investigational procedure would not be classified as an SAE. An example of this would be angioplasty to treat a patient's underlying CAD. Events resulting from the investigational procedure or a worsening of a pre-study condition which satisfy the definition of a SAE must be reported.

6.10.6.2 Reporting Serious Adverse Events

All SAEs, whether related or unrelated to the investigational product, must be reported within 1 calendar day to LMI Drug Safety by confirmed facsimile transmission, email or phone. Overnight express mail may also be used in lieu of a facsimile transmission. If only limited information is initially available, follow-up reports are required. The original SAE form must be kept on file at the study site.

Collection of complete information concerning SAEs is extremely important. Thus, follow-up information that becomes available as the SAE evolves, as well as supporting documentation (e.g., hospital discharge summaries and autopsy reports), should be collected subsequently, if not available at the time of the initial report, and immediately sent using the same procedure as the initial SAE report.

The contact information for reporting SAEs and follow-up SAE information is:

Contact	Telephone Number	Fax Number	Email Address
LMI Safety	[name] + [contact]	[contact]	[contact]

If the investigator needs to discuss an SAE or any other aspect of the protocol with the Medical Monitor, s/he can be reached at the following numbers:

LMI Medical Monitor
24-Hour [contact]
[contact]

In the event of AEs that are serious, unexpected, and possibly related or related to DEFINITY® administration, LMI will contact the Investigator and will provide a MedWatch and/or Council for International Organizations of Medical Sciences (CIOMS) narrative of the case, which will include an Analysis of Similar Events. The Investigator is responsible for notifying the appropriate IRB in accordance with institutional requirements. The Investigator and IRB will determine if the IC requires revision. The Investigator should also comply with the IRB procedures for reporting any other safety information.

6.11 Removal of Subjects from the Trial or Investigational Product

The investigator may withdraw a patient from the study for any of the following reasons:

- Patient withdraws consent
- Patient is lost to follow up
- Patient has an AE that, in the opinion of the Investigator, requires the patient's discontinuation
- Discretion of the Investigator
- The Sponsor or Investigator terminates the study

All events that result in discontinuation of study treatment will be appropriately recorded and reported. In addition, for all subjects who discontinue prematurely, an evaluation which reflects the status of the patient at premature termination, along with a final assessment and the reasons for termination, will be recorded on the eCRF.

7 QUALITY CONTROL AND ASSURANCE

The sponsor has implemented and maintains Quality Assurance and Quality Control systems with written procedural documents (e.g. SOPs, work instructions, monitoring plans, etc.) to ensure that the study is conducted, and data are generated, recorded, and reported in compliance with the protocol, ICH-GCP, and all applicable regulatory requirements.

These quality systems include monitoring (see Section 9.6); data collection, review and entry (see Section 9.11); training; and audit by the sponsor's Quality group or representative. Audits are independent of routine monitoring and quality control functions, and are conducted to evaluate trial conduct and compliance with the protocol, procedural documents, ICH-GCP and applicable regulatory requirements.

8 PLANNED STATISTICAL METHODS

8.1 Statistical Analyses

8.1.1 General Considerations

The contract research organization (CRO) will be responsible for data management and statistical analysis in this trial. All statistical analyses will be performed using SAS (SAS Institute, Inc., Cary, NC) version 9.4 or higher. Patient data listings and tabular presentations of results will be provided. Presentation of summary statistics for continuous variables will include N, mean, median, and standard deviation, as well as the minimum and maximum values. For categorical variables, the number and percent of each category within a parameter for non-missing data will be calculated. All statistical tests will be two-sided employing a significance level of 5% unless otherwise specified. Further details of the criteria and conduct of the statistical analyses are below and will be included in the Statistical Analysis Plan for this study.

8.1.2 Analysis Populations

8.1.2.1 Safety Population

The Safety Population (SP) will include all subjects who have signed informed consent and who have received any amount of DEFINITY® in the study. This is the primary analysis population for the safety analysis.

8.1.2.2 Intent-to-Treat

The Intent-to-Treat (ITT) population will include all subjects who have signed informed consent.

8.1.2.3 Modified Intent-to-Treat Population

The Modified Intent-to-Treat (mITT) population will include all ITT subjects who complete unenhanced imaging, DEFINITY®-enhanced imaging, and cardiac MR studies. This is the primary analysis population for the efficacy endpoints.

8.1.2.4 Per-Protocol Population

The Per-Protocol (PP) population will include all subjects in the mITT population who a) did not violate inclusion and exclusion criteria that would likely have an effect on the primary outcome, b) do not have major protocol violations; c) have LVEF data on both unenhanced and DEFINITY®-enhanced for at least one reader; (d) have CMR LVEF.

Efficacy analyses will be conducted for both mITT and PP population sets. Differences in results using the two populations will be carefully examined and the results of that evaluation presented in the study report.

8.2 Efficacy Endpoint(s)

8.2.1 Primary Efficacy Endpoint

The primary analysis is to demonstrate an improvement in LVEF accuracy from unenhanced imaging to imaging with DEFINITY® contrast enhancement using CMR as the truth standard. For each patient, the absolute value of the difference of DEFINITY® LVEF minus CMR LVEF will be calculated. Similarly, the absolute value of the difference of unenhanced imaging LVEF minus CMR LVEF will be calculated for each patient. The primary analysis is to assess the significance of the difference between DEFINITY® and unenhanced echo with respect to the mean “absolute value of the difference vs. CMR”. These means will be compared with a paired t-test at a two-sided 0.05 level of significance. Specifically, the null and alternative hypotheses are:

$$H_0: \mu_D = \mu_U \text{ vs. } H_1: \mu_D \neq \mu_U$$

where μ_D and μ_U are the mean of the DEFINITY® and unenhanced echo absolute value of the difference vs. CMRs, respectively. A sample of size 150 enrolled subjects has 90% power to reject the null hypothesis in favor of the alternative if the true difference $\mu_D - \mu_U$ is at least 2.75 (in favor of DEFINITY®) with a standard deviation of 10 or less and allows for approximately 5% premature withdrawal.

The analyses will be conducted separately for each of the three blinded readers of the DEFINITY® enhanced and unenhanced images; the criterion for success is that the null hypothesis is rejected in favor of DEFINITY® for at least 2 of the 3 blinded readers. CMR LVEF is interpreted by a single reader; this is the CMR LVEF that will be used as the comparator for each of the three blinded readers.

The primary analysis will be performed on mITT subjects with non-missing LVEF for DEFINITY®, unenhanced echocardiography, and the reference standard. A supportive analysis will be run where a missing echocardiography or CMR LVEF is multiply imputed using the fully conditional specification (FCS) multiple regression, as outlined below and as will be further detailed in the Statistical Analysis Plan.

The following are additional analyses to be carried out separately for each blinded reader to achieve the primary objective:

Bias is the mean of the actual (not absolute value) per-subject differences between the imaged LVEF and CMR LVEF. The bias, the two-sided 95% confidence interval of the bias,

the precision (standard deviation of the per-subject differences) and the root mean square error (RMSE) will be calculated for DEFINITY®. The RMSE is the square root of the bias-squared + precision-squared and is considered a measure of overall accuracy. These analyses will be repeated for unenhanced echocardiography vs. CMR. It is anticipated that the RMSE will be smaller for DEFINITY®-enhanced LVEF than for unenhanced LVEF.

DEFINITY®-enhanced and unenhanced echocardiography LVEF will each be assessed for measurement accuracy against the reference CMR using Bland-Altman analysis and Deming regression analysis. For the Bland-Altman analysis, a plot of the per-subject difference between DEFINITY®-enhanced echocardiography and CMR LVEF will be plotted vs. the per-subject sum of the two measurements. Limits of agreement (defined as the mean of the DEFINITY® vs. CMR difference) +/- 2 SD will be shown on the plot. The same analyses will be performed for unenhanced echocardiography using CMR as the reference standard.

Deming regression plots of LVEF vs. CMR LVEF will be generated for each of DEFINITY®-enhanced and unenhanced echocardiography. Unweighted Deming regression will be employed to estimate the regression slope and intercept with two-sided 95% confidence intervals of each assuming the measurement error is the same for CMR and each of the echocardiography error techniques.

The intra-class correlation coefficient (ICC) and its two-sided 95% confidence interval will be calculated for DEFINITY®-enhanced echo vs. CMR and for unenhanced echo vs. CMR. The ICCs and their two-sided confidence intervals will be calculated using between and within mean squares from an ANOVA model with method (echocardiography, CMR) and subject as the main effects and LVEF as the dependent variable. The ICC will be calculated using the SAS macro developed by Hamer (1990).⁷

Assessment Across Study Centers: The mean “absolute value of the difference vs. CMR” for each DEFINITY® and unenhanced echocardiography, as well as the difference between the two treatments with respect to this mean, will be presented for each study center and blinded reader. Within each blinded reader, an assessment of study center effect on the mean treatment difference will be carried out using one-way analysis of variance. For each blinded reader, a site difference that is not significant at the 0.15 level of significance, or a site difference that is significant but where for every site the mean treatment difference is more favorable for DEFINITY® than enhanced echocardiography, will support pooling subjects across sites for the primary analysis for that reader.

Missing Data: Within each blinded reader, the primary analysis will be performed on subjects with non-missing LVEF for DEFINITY®, unenhanced echocardiography, and the reference standard. A supportive analysis will be run where, within each blinded reader, missing LVEF is multiply imputed using the fully conditional specification (FCS) multiple regression. The covariates in the imputation model will be fully specified in the formal

statistical analysis plan and will include baseline and demographic variables and will also include imaging method (DEFINITY®, unenhanced, or CMR reference standard). A total of 50 imputations will be generated; the paired t-test comparing mean bias between DEFINITY® and unenhanced will be performed separately on each of the 50 imputed datasets, and the t-test results will be combined across datasets using the usual multiple imputation techniques to create one overall paired t-test results on imputed data.

